### **4.5 Pharmacodynamic Set**

The Pharmacodynamic Analysis Set consists of all enrolled subjects who do not have major protocol violations that affect the validity of the PD results, receive at least 1 dose of rhPTH(1-84) and have at least 1 evaluable post-dose pharmacodynamic value available for 1 dose regimen. Subjects who do not meet the inclusion criterion for hypoparathyroidism will be excluded from the PD set. A listing of subjects excluded from the PD Set along with the reason for exclusion is to be generated. In the event of dosing error, proven or suspected based on PK data (extremely low post-dose PTH concentrations), PD data from the subject for the specific treatment period will be excluded. During treatments A, B, and C, if a subject takes supplemental oral calcium/active vitamin D within 24 hours post the last rhPTH(1-84) dose, PD data from the subject for the specific treatment period will be excluded from summary tables and figures. A listing of excluded PD data along with the reason for exclusion will be generated.

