On Day 1 of Treatment Period 2, subjects will receive the alternative treatment (according to the randomization schedule), following a washout period ( $\geq 5$  days [ie, 120 hours] and  $\leq 30$  days) between administration of the dose or first dose ([for once-daily or twice-daily dosing, respectively] of each treatment period). All investigational product will be administered via SC injection into alternating thighs at each administration.

At each treatment period, subjects will report to the CRC on Day-2, remain in the CRC through Day 2, and be discharged following the last scheduled assessment on Day 2 (investigators may elect, at their discretion, to keep the subject in-clinic after Treatment Period 1 for the duration of the washout period, eg, if the washout period is short [eg, 120-172 hours] or there are any safety concerns).

For once-daily treatments (Treatments B and E), subjects will receive a single subcutaneous dose of rhPTH(1-84) in the morning on Day 1. For twice-daily treatments (Treatments A, C, D, and F), subjects will receive a subcutaneous dose of rhPTH(1-84) in the morning followed by the second dose 12 hours later on Day 1 (in the opposite thigh). If randomized to rhPTH(1-84) with calcium, subjects will take their usual supplemental oral calcium on Day 1 per their usual schedule. Prior to discharge from the CRC at each treatment period, subjects will be given specific instructions for when to take their supplemental oral calcium and active vitamin D supplements during the day(s) when subjects are not in the CRC.

Subjects enrolled in the study must require daily doses of calcium supplements of  $\geq 1000$  mg prior to baseline (Day 1). Subjects enrolled in the study must also require minimum daily doses of active vitamin D of  $\geq 0.25\mu\text{g}$  (ie,  $0.25\mu\text{g}$  calcitriol or equivalent). Subjects will be expected to adhere to standard meals provided during their confinement in the CRC during each period (from check-in on Day -2 until discharge on Day 2). All subjects (in all treatments) will take their usual doses at the usual regimen of supplemental oral calcium and active vitamin D on Day -2 and Day -1. For all subjects in all cohorts, active vitamin D supplements must be withheld on Day 1 through completion of all study procedures on Day 2. Subjects may resume active vitamin D following final procedures on Day 2 at the discretion or direction of the investigator.

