During Treatments A, B, and C (Cohorts 1 and 2), supplemental oral calcium and active vitamin D will be withheld starting on Day 1 (predose), through the completion of all study procedures on Day 2 for both the once-daily and twice-daily dosing regimens. Upon completion of all study procedures on Day 2, subjects will then resume their usual supplemental oral calcium and active vitamin D at their next usual daily schedule.

During Treatments D, E, and F (Cohorts 3 and 4), subjects will withhold active vitamin D on Day 1 but take their usual dose(s) of supplemental oral calcium according to their usual regimen, regardless of the schedule/timing of investigational product administration(s).

Critically, oral calcium supplementation should be identical on Day -1, Day 1 and Day 2 in Treatment Period 1 and Treatment Period 2. On Day 2, subjects will continue with their usual supplemental calcium regimen (ie, identical on Day -1 and Day 1), and, following the completion of all study procedures, subjects will then re-start their active vitamin D at their next usual daily schedule.

During the washout period, subjects will be instructed to take their usual doses of supplemental oral calcium and active vitamin D.

Any subject who experiences symptoms of hypocalcemia or hypercalcemia may be treated at the investigator's discretion, as per local standards. This may include, but is not limited to, intravenous (IV) calcium and/or fluids.

For all dosing regimens, rhPTH(1-84) will be administered in the morning of Day 1 of each treatment period following an overnight fast of at least 8 hours. Subjects will continue to fast until approximately 2 hours after rhPTH(1-84) administration, at which time a standardized meal will be served (see Section 4.3 item 5). For subjects assigned to the twice-daily dose regimen, the evening dose of investigational product will be administered 12 hours after the morning dose, and 2 hours prior to the evening meal. A snack or light meal may be provided to the subjects prior to the evening dose, provided it is consumed  $\geq 2$  hours prior to investigational product dose administration. It is suggested that lunch be divided into 2 portions, the first portion consumed at lunch, and the second portion consumed as the snack or light meal.

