**Table 2: Schedule of Assessments**

Study Visit	Screening		Predose Assessment		Treatment Period 1		Washout	Predose Assessment		Treatment Period 2		Follow-up
	Admin.	Clinical	TP1, D-2	TP1, D-1	TP1, D1	TP1, D2	W a,b	TP2, D-2	TP2, D-1	TP2, D1	TP2, D2	FU
Study Relative Day/ Study Procedures	-120 to -03	-28 to -03	-2	-1	1	2		-2	-1	1	2	Follow-up c

be kept in cold conditions (~4°C) and returned to the CRC upon collection, as per the instructions provided by the site.

q A 24-hour urine sample should be collected and provided to the site anytime during the Clinical Screening Period, but provision of the sample should be no later than check-in to the CRC at Period 1, Day -2.

r Adverse events to be collected from time of informed consent. This includes the period of an administrative screen, if utilized.

s Applies to subjects assigned to Treatment A, Treatment B and Treatment C only.

t Supplemental oral calcium and active vitamin D will be withheld starting on day of dosing, and through the end of Day 1. Subjects will then resume their usual supplemental oral calcium and active vitamin D at their next usual daily schedule on Day 2.

u Applies to subjects assigned to Treatment D, Treatment E and Treatment F only.

v Supplemental oral calcium should be taken according to the subject's usual daily regimen (but active vitamin D must be withheld).

HBsAg=hepatitis B surface antigen; HCV=hepatitis C virus; HIV=human immunodeficiency virus

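### SAP 4.5's automatic exclusion of PD data for active vitamin D intake covers only Treatments A, B and C, although active vitamin D is withheld in all six treatments

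*SAP*

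**What the plan says.** SAP 4.5 (Pharmacodynamic Set) sets the rule: "During treatments A, B, and C, if a subject takes supplemental oral calcium/active vitamin D" in the 24 hours after the last rhPTH(1-84) dose, then "PD data from the subject for the specific treatment period will be excluded from summary tables and figures". Neither that section nor any other part of the SAP gives a counterpart for Treatments D, E and F.

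The other route for a protocol violation is the entry condition of the set, repeated in SAP 12.1: subjects qualify if they "do not have major protocol violations that affect the validity of the PD results". It applies whatever the treatment, but it decides membership for the whole subject, leaves major undefined and does not name active vitamin D.

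The withholding requirement is wider than the exclusion rule. Protocol 3.1 states: "For all subjects in all cohorts, active vitamin D supplements must be withheld on Day 1 through completion of all study procedures" on Day 2. It then repeats, "During Treatments D, E, and F (Cohorts 3 and 4), subjects will withhold active vitamin D on Day 1", with usual oral calcium continued. SAP 2.1 says the same for D–F, with restart after the Day 2 procedures, and the note under its treatment scheme describes all treatments as without active vitamin D. Footnote v of the SAP Schedule of Assessments, which applies to D–F, says "but active vitamin D must be withheld".

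**The concern.** The sentence in SAP 4.5 joins two triggers with a slash, so the vitamin D trigger inherits a limit that suits only calcium.

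The primary objective includes the effect of supplemental oral calcium. Subjects may join only one cohort, so that effect can be read only between subjects, A–C against D–F. The difference in rules falls exactly along that line.

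Two features of the study make a retained violator relevant:

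- The protocol's abbreviation list equates calcitriol with 1,25(OH)2D3, which is itself a PD marker with its own parameters and tables. An ingested dose could be summarised as a response to rhPTH(1-84).
- Protocol 1.1 says active vitamin D is given to improve gastrointestinal calcium absorption, and D–F are the treatments in which oral calcium continues.

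Intake in only one of a D–F subject's two periods could also disturb the within-subject comparison of twice-daily with once-daily dosing.

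**Working it through.** The plan states no figure to reproduce: the study is descriptive, with no power calculation or hypothesis test (SAP 2.5, 2.6). The check is mainly a comparison of texts.

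**1. Restriction against exclusion rule**

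| Treatments | Oral calcium | Active vitamin D | Automatic PD exclusion for calcium | Automatic PD exclusion for active vitamin D |
|---|---|---|---|---|
| A, B, C (Cohorts 1–2) | withheld | withheld | yes | yes |
| D, E, F (Cohorts 3–4) | continued | withheld | no, consistent | **no, inconsistent** |

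Active vitamin D is prohibited in 6 of 6 treatments; the rule reaches 3 of 6.

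**2. What one violation leads to**

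- In A–C, that period's PD data leave the summary tables and figures without any discretionary step.
- In D–F, either nothing happens or the major-violation clause is invoked. As that clause defines who is in the set, its natural reading removes the subject, including a period with no deviation.

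**3. The window**

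The last scheduled PD blood sample is at 24 h in a once-daily period and at 36 h in a twice-daily period (SAP detailed schedules). The second twice-daily dose is at 12 h, and 12 + 24 = 36. The SAP 4.5 window therefore ends at the last PD sample under both regimens, and its end point is worth keeping. Read literally, it starts only at the last dose, which in a twice-daily period is 12 hours after the first, so the start should be stated.

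**4. Planned numbers outside the automatic rule**

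- Subjects: 4 cohorts × 8 = 32 in total; Cohorts 3 and 4 contribute 2 × 8 = 16.
- Periods: 32 × 2 = 64 in total; Cohorts 3 and 4 contribute 16 × 2 = 32.

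**5. Leverage of one subject**

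If k of n subjects in a treatment are retained violators and each value is shifted by δ, the treatment mean shifts by kδ/n. With k = 1:

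- D or F, n = 8: δ/8 = 0.125δ.
- E pooled over Cohorts 3 and 4, n = 16: δ/16 = 0.0625δ.

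The documents supply neither k nor δ, so the calculation stops here.

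**The case against.** The case against making much of this has five parts.

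- **The general clause.** A reader might infer that D–F have no vitamin D rule at all. The documents do not support that. The major-violation clause covers every treatment, and taking a prohibited supplement during PD sampling could fall under it. What D–F lack is an explicit, automatic, period-level rule.
- **A–C are not guaranteed the milder outcome.** A reader might infer that a violation in A–C costs exactly one period. The general clause applies there too, and nothing in SAP 4.5 says the specific sentence displaces it.
- **Low opportunity.** Subjects are confined to the research centre from Day -2 to Day 2, and no expected frequency of intake is given.
- **Visibility.** Deviations are listed (SAP 6), calcium and vitamin D use has its own listing (SAP 9), and excluded data appear in Listing 5.11. PD summaries may also be run with and without potential outliers (SAP 12.4).
- **No formal contrast.** PD output is descriptive by treatment and day. Subjects are randomised only to sequence within sequential cohorts, so any calcium comparison is already between non-randomised groups.

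The first two points limit the wording and the next two limit the likely impact. None removes the mismatch. Listings show a violation but do not settle how the summaries treat it. In an open-label study whose outlier exclusions are decided case by case after database lock, leaving this to discretion on one side only is avoidable.

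**Conclusion.** The mismatch stands. SAP 4.5 limits its automatic exclusion for active vitamin D to three of the six treatments in which active vitamin D is prohibited, so the with-calcium and no-calcium treatments are cleaned by different rules. This is a stated rule with the wrong scope, and it should be corrected.

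On planned numbers, 16 of 32 subjects and 32 of 64 periods lie outside the rule. The fractions 1/8 (12.5%) and 1/16 (6.25%) are one subject's weight in a mean, assuming exactly 8 evaluable subjects per cohort. They are not estimates of bias.

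A reader might go further and infer that vitamin D effects will be counted as effects of oral calcium. That would need at least one D–F violator, no use of the general clause, a material vitamin D effect within the sampling window, and someone reading D–F against A–C. The documents establish none of the first three, so distortion of the primary objective is possible but not shown.

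**What to change.** Split the sentence in SAP 4.5 and keep the end of the existing window:

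1. In all treatments A–F, if a subject takes active vitamin D at any time from Day 1 until 24 hours after the last rhPTH(1-84) dose of the period, that period's PD data are left out of summary tables and figures.
2. In A, B and C only, the same applies to supplemental oral calcium.

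Report both kinds of exclusion, with the reason, in Listing 5.11. Keep the 24-hour limit rather than referring to the withholding period, because the documents do not define that period consistently.

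The cost is a short SAP edit and possibly a few D–F periods. No new data are needed: Protocol 5.2 already requires times and doses of calcium and active vitamin D in the CRF for Days -1, 1 and 2 of both periods.

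Separately, the withholding instructions must be reconciled. Footnote t of the Schedule of Assessments (Protocol Table 1 and the SAP) ends withholding in A–C with Day 1 and lets supplements resume on Day 2. The text of Protocol 3.1 and SAP 2.1 runs it until all Day 2 procedures are done. For D–F, the schedule row is marked on Day 1 only, while the text extends to Day 2. Until this is settled, a subject who follows footnote t could still meet the SAP 4.5 exclusion, most obviously in a twice-daily period, where the window runs to 36 hours.

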On Day 1 of Treatment Period 2, subjects will receive the alternative treatment (according to the randomization schedule), following a washout period (≥5 days [ie, 120 hours] and ≤30 days) between administration of the dose or first dose ([for once-daily or twice-daily dosing,

respectively] of each treatment period). All investigational products will be administered via SC injection into alternating thighs at each administration.

At each treatment period, subjects will report to the CRC on Day-2, remain in the CRC through Day 2, and be discharged following the last scheduled assessment on Day 2 (investigators may elect, at their discretion, to keep the subject in-clinic after Treatment Period 1 for the duration of the washout period, eg, if the washout period is short [eg, 120-172 hours] or there are any safety concerns).

For once-daily treatments (Treatments B and E), subjects will receive a single subcutaneous dose of rhPTH(1-84) in the morning on Day 1. For twice-daily treatments (Treatments A, C, D, and F), subjects will receive a subcutaneous dose of rhPTH(1-84) in the morning followed by the second dose 12 hours later on Day 1 (in the opposite thigh). If randomized to rhPTH(1-84) with calcium, subjects will take their supplemental oral calcium within 30 minutes prior to first dose administration. Prior to discharge from the CRC at each treatment period, subjects will be given specific instructions for when to resume taking their supplemental oral calcium and active vitamin D supplements during the day(s) when subjects are not in the CRC.

Subjects enrolled in the study must require daily doses of calcium supplements of  $\geq 1000$  mg prior to baseline (Day 1). Subjects enrolled in the study must also require minimum daily doses of active vitamin D of  $\geq 0.25\mu\text{g}$  (ie,  $0.25\mu\text{g}$  calcitriol or equivalent). Subjects will be expected to adhere to standard meals provided during their confinement in the CRC during each period (from check-in on Day -2 until discharge on Day 2). All subjects (in all treatments) will take their usual doses of supplemental oral calcium and active vitamin D on Day -2 and Day -1.

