During Treatments A, B and C, supplemental oral calcium and active vitamin D will be withheld starting on Day 1 (pre-dose), through the completion of all study procedures on Day 2 for both the once-daily and twice-daily dosing regimens. Upon completion of all study procedures on Day 2, subjects will then resume their usual supplemental oral calcium and active vitamin D at their next usual daily schedule.

During Treatments D, E and F, subjects will take their usual dose of supplemental oral calcium (but withhold active vitamin D) in the morning on Day 1, prior to investigational product administration. On Day 2, following the completion of all study procedures, subjects will then re-start their active vitamin D at their next usual daily schedule.

During the washout period, subjects will be instructed to take their usual doses of supplemental oral calcium and active vitamin D.

Any subject who experiences symptoms of hypocalcemia or hypercalcemia may be treated at the investigator's discretion, as per local standards. This may include, but is not limited to, intravenous (IV) calcium and/or fluids.

For all dosing regimens, rhPTH(1-84) will be administered in the morning of Day 1 of each treatment period following an overnight fast of at least 8 hours. Subjects will continue to fast

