#### **12.4.3 Serum Pharmacodynamic Parameters**

Pharmacodynamic parameters will be computed from the individual raw concentrations of serum calcium (mmol/L) (uncorrected and corrected for serum albumin levels), phosphate (mmol/L), magnesium (mmol/L), 1,25(OH)2D3 (pmol/L) and FGF23 using a non-compartmental approach and actual times. pharmacodynamic parameters will be estimated for both Day -1 and Day 1 in each treatment period. Serum calcium will be corrected for serum albumin levels using the following equation:

Corrected calcium (mmol/L) = serum calcium (mmol/L) + 0.02 (40 - serum albumin (g/L))  
(Parent X1, 2009)

The following parameters will be calculated from the raw serum concentration data using WinNonlin Phoenix version 6.3 or higher (Pharsight Corporation, Mountain View, California, USA):

- AUC0-24h: the area under the concentration versus time curve, from time 0 to 24 hours
- TEmax: time to maximum effect
- Emax: maximum effect
- TEmin: time to minimum effect
- Emin: minimum effect

The same parameters will also be calculated for the calcium-phosphate product.

In addition, serum pharmacodynamic parameters will be estimated based on baseline-adjusted serum concentration of pharmacodynamic markers as follows:

- AUCabove: Area under the concentration-time curve that is above the baseline, from time 0 to 24 hours, as calculated by the linear trapezoidal method
- AUCbelow: Area under the concentration-time curve that is below the baseline, from time 0 to 24 hours, as calculated by the linear trapezoidal method
- AUCnet: AUCabove - AUCbelow
- TEmax: time to maximum effect
- Emax: maximum effect
- TEmin: time to minimum effect
- Emin: minimum effect

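### SAP 4.5 starts the supplement exclusion window at the last dose, so intake in the first 12 hours removes a once-daily period but does not trigger the rule in a twice-daily period

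*SAP*

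**What the plan says.** SAP 4.5 (Pharmacodynamic Set) contains one rule on supplements. It applies to Treatments A, B and C and is triggered "if a subject takes supplemental oral calcium/active vitamin D within 24 hours post the last rhPTH(1-84) dose". The consequence is that "PD data from the subject for the specific treatment period will be excluded from summary tables and figures".

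SAP 2.1 fixes the dose times. In the once-daily treatments "subjects will receive a single subcutaneous dose of rhPTH(1-84) in the morning on Day 1". In the twice-daily treatments "subjects will receive a subcutaneous dose of rhPTH(1-84) in the morning followed by the second dose 12 hours later on Day 1".

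SAP 2.1 also sets the conduct rule for these three treatments: both kinds of supplement "will be withheld starting on Day 1 (pre-dose), through the completion of all study procedures on Day 2". It states that this covers both regimens.

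No other section gives a supplement-intake exclusion. SAP 12.1 repeats the general definition of the PD set and refers the reader to Section 4.4, which is the pharmacokinetic set. Protocol 9.7 has no such exclusion.

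**The concern.** The exclusion should remove periods in which prohibited supplements could have altered serum or urinary calcium, and it should do so in the same way for both periods of the crossover. Because the window is tied to the last dose, it opens 12 hours later in a twice-daily period. The same breach at, say, hour 4 or hour 8 is then handled in opposite ways in the two periods of one subject.

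Control of serum calcium and urinary calcium excretion is the PD part of the primary objective (SAP 3.1). The serum parameter is defined as "the area under the concentration versus time curve, from time 0 to 24 hours", and SAP 12.4.4 totals urinary excretion over 24 hours after dosing. The uncovered hours are the first half of both. At the minimum cohort size of 8, one subject carries 1/8 = 12.5% of a Treatment A or Treatment C mean, so a single period kept or dropped inconsistently is visible in the summary.

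**Working it through.** All times are hours from the first dose of the period. I take time 0 of AUC0-24h, and the start of the 24-hour urine total, as the first dose.

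**Inputs.** Last dose: 0 h in B, 12 h in A and C (SAP 2.1). Window length: 24 h (SAP 4.5). PD collection ends at 24 h once daily and 36 h twice daily (SAP detailed schedules for the two regimens).

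**Formula.** Literal window = [last dose, last dose + 24 h].

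- Once daily: 0 to 0 + 24 = 24 h.
- Twice daily: 12 to 12 + 24 = 36 h.

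The upper ends reproduce the plan's own ends of PD collection, 24 h and 36 h. Only the lower ends are at issue.

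| Intake at | Breaches SAP 2.1? | Once daily (B) | Twice daily (A, C) |
|---|---|---|---|
| Day 1, before first dose | yes | not triggered | not triggered |
| 0.5, 4, 8 or 11.9 h | yes | period excluded | not triggered |
| 12.1, 20 or 23.9 h | yes | period excluded | period excluded |
| 26 or 35 h | twice daily only (once-daily sampling is over) | not triggered | period excluded |

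**Size of the gap in A and C.**

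- Share of the 0-24 h window: 12/24 = 50%; for B it is 0/24.
- Post-dose serum PD samples up to 24 h: 1.5, 4, 6, 8, 10, 12, 13.5, 16, 18, 20, 22 and 24 h, which is 12. Six of them (1.5 to 12 h) are drawn by the second dose.
- Urine intervals in 0-24 h: seven. Four of them (0-3, 3-6, 6-9 and 9-12 h) end by the second dose.
- Planned periods in which the gap exists: at least 8 in A and 8 in C, so 16, against 16 in B where it does not. These are periods exposed to the gap, not periods with intake.

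**Two further points.** Day 1 pre-dose intake is missed in A, B and C alike: it is a gap, but not a difference between regimens. Separately, footnote t of the SAP's Table 2 (Schedule of Assessments) has supplements withheld to the end of Day 1 and resumed on Day 2, whereas SAP 2.1 withholds them until Day 2 procedures are complete. After a morning first dose, 36 h is the evening of Day 2. A twice-daily subject who follows footnote t could therefore take supplements inside the exclusion window and lose the period.

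**The case against.** The strongest reply is that the phrase marks only an end. The sentence opens by naming the treatments, and 24 hours after the last dose coincides with the end of PD collection in both regimens. The authors may have meant any intake during treatment up to that time. This is plausible, but the sentence states no start, and a programmer applying it as written would obtain 12-36 h for A and C. If the end-point reading was intended, the correction merely records it.

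A second reply is that such intake would not go unnoticed. SAP 4.5 also leaves out subjects with major protocol violations that affect PD validity. SAP 6 lists all deviations, SAP 9 gives calcium and vitamin D their own listing, and SAP 12.4 provides for outlier review. A reader might infer from the gap that a twice-daily period with early intake always stays in the tables; because of the violations clause, the documents do not support that. But the clause does not define major, does not name supplements, and removes the subject rather than the period. The listings and the review are not exclusion rules.

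A third reply concerns direction. A reader might infer that the gap raises twice-daily calcium relative to once-daily. That is not established. SAP 2.1 lets investigators treat symptomatic hypocalcemia. If intake follows low calcium, excluding the once-daily period removes a low-calcium subject and may raise that mean as well. The sign depends on why the supplement was taken.

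Finally, subjects are confined from Day -2 to Day 2, so intake may be uncommon, and the analyses are descriptive with no hypothesis test. Both are true; they limit the consequence but do not make the rule consistent.

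**Conclusion.** As written, the rule filters the two regimens differently. For A and C it leaves uncovered 12 of the 24 hours behind the serum AUC and the 24-hour urine totals; for B it leaves none. This rests on the literal wording of SAP 4.5 and the 12-hour dose interval, and on no assumption about drug effect.

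The size of any bias cannot be stated. The documents give neither the frequency of prohibited intake nor the calcium response to it, so a figure in mmol/L would be pure assumption. A reader might also take the 16 twice-daily no-calcium periods as affected; only those with intake at 0-12 h would be, and that number is unknown. The point is a modest one that should be corrected before database lock, because it is cheap and there is no prespecified fallback.

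**What to change.** In SAP 4.5, replace the window with: *at any time from Day 1 pre-dose to 24 hours after the last rhPTH(1-84) dose of that period*, for once-daily and twice-daily treatment alike. Keep the exclusion of the whole period.

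The window after the first dose then runs 0-24 h once daily (unchanged) and 0-36 h twice daily, with the same pre-dose start in both. Intake at any time in 0-12 h is treated the same way. The ends still differ, in line with the different ends of PD collection.

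The cost is one sentence and possibly some data: a twice-daily period with intake at 0-12 h, or any A, B or C period with Day 1 pre-dose intake, would leave the PD tables and figures. No new data are needed, since Protocol 5.2 already requires calcium and active vitamin D administration times to be recorded for Days -1, 1 and 2.

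Footnote t of the SAP's Schedule of Assessments must also be reconciled with SAP 2.1, so that a subject who follows one instruction is not excluded under the other.
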